9.0 Data and Safety Monitoring Plan

9.1 Periodic evaluation of data

The PI and research staff will be responsible for the daily oversight of subject safety. Subjects will be seen by research staff while in the study that will assess adverse events and take appropriate medical actions if necessary. The Safety Monitor will review AEs on a weekly basis and study staff will discuss subject's experiences during meetings when necessary. The Safety Monitor will consult with the study pulmonologist ([name]) on respiratory related adverse events. In addition, the study statistician will prepare a cumulative report of all data points listed below for the Data and Safety Monitoring Committee to review every 6 months after recruitment begins.

9.2 Data that are reviewed

The Data and Safety Monitoring Report will include:

- Accrual and retention
- Baseline sociodemographic characteristics
- Adverse events and serious adverse events
- Protocol deviations/violations
- Participants' ability to achieve study requirements

- Significant changes in mental health status including suicidal ideation
- Changes in psychological measures of anxiety and depression (OASIS and QIDS)
- Changes in cigarette consumption from baseline
- Exhaled carbon monoxide increase from baseline
- Changes in lung function via pulmonary lung function tests
- Changes in lung function via the Clinical COPD questionnaire

9.3 Method of collection of safety information

Safety data and adverse event information will be collected at study visits and entered directly into REDCap. Every study visit, participants will be asked a series of standard questions that would trigger an assessment for an adverse event to be documented. Adverse event information can also be given voluntarily by participants between study visits. An adverse event log will be used to document the description of the adverse event including, start/stop dates of event, type, grade, attribution to the study treatment, expected/unexpected, and action taken.

9.4 Frequency of data collection

Adverse event information and safety data will be collected at each study visit but can be reported at any time during the study.

9.6 Frequency of review of cumulative data

A Data and Safety Monitoring Report with cumulative data will be generated every 6 months after recruitment begins.

9.7 Statistical tests

Basic descriptive statistical methods will be used to analyze the safety data to determine whether harms are occurring. Changes from the baseline in cigarette consumption, exhaled carbon monoxide, pulmonary function, and mental health measures will be calculated. In addition, the accrual and retention-dropout rate, completion rate, and the proportions of adverse events (AE) and serious adverse events (SAE) will be generated.

9.8 Suspension of research

Due to the low risk of the study treatment, it is unlikely that there will be a need to suspend the research. However, should the committee identify any issues after reviewing the cumulative data, these recommendations will be followed.

10.0 Risks

Switching cigarette brands: Before being randomized in the study you will switch from your usual brand of cigarettes to study cigarettes that are similar in nicotine to your own brand of cigarettes to smoke for 2 weeks. The cigarettes you are given throughout this study may have different characteristics (i.e. nicotine level, ventilation, length, etc.) than your usual brand. So you could experience symptoms related to different strength or sensory effects from the study cigarettes, such as harshness in your throat or chest.

Increased compensatory smoking: Participants may be given cigarettes that have very low levels of nicotine in them which may lead to compensatory smoking and in turn increased levels of toxicant exposure. In prior studies, compensatory smoking was minimal and higher levels of toxicant exposure were generally not observed. Cigarette consumption and exhaled carbon monoxide will be monitored throughout the trial.

E-cig use: There may be some unknown risks related to the use of e-cigs. The most common side effects associated with using an e-cig are changes in taste, dehydration, mucus in throat/sinus, dry mouth, dry cough, throat irritation, mouth irritation, sore throat, mouth ulcers, dizziness, headache, nausea, and hiccups.

- E-cig liquid contains vegetable glycerin, propylene glycol, and flavorings. It is possible that participants may have an allergy to one of more of these ingredients. Participants with known allergies to these substances will be excluded from the study. The most common reported allergic reaction to these substances is contact dermatitis (or rash).
- There are reports that some people who use e-cigarettes have experienced seizures, with most involving youth or young adult users. Participants with a history of seizures or take medications to prevent seizures will be excluded from the study.
- There have been some reports of serious lung illnesses among those who used e-cigarettes, and even some cases of death as a result. The cause of all deaths has not been identified. The investigations being conducted by the Centers for Disease Control and Prevention (CDC) and the Food and Drug Administration (FDA) have found that the majority of people experiencing these illnesses were using e-cigarette products that contained tetrahydrocannabinol (THC) and/or products that were bought off the street and not from retail establishments. The e-cigarette products used in this study do not contain THC and were bought from manufacturers where quality testing and control is performed. Nonetheless, participants will be advised to call their doctor immediately if they experience cough, shortness of breath, chest pain, nausea, vomiting, diarrhea, or fever after using their e-cigarette. Participants will be told to only use the e-cigarette and liquid pods (cartridges) given to them by the researchers and to not tamper with their e-cigarette or use other liquids with the e-cigarette device.

Nicotine addiction: Participants may be given an e-cig that contains nicotine, which is an addictive substance.

The amount of nicotine they receive from this product depends on what product they are given and how they use it.

Nicotine withdrawal symptoms: Ceasing nicotine may result in nicotine withdrawal symptoms (e.g., irritability, anxiety, restlessness, depressed mood, increased appetite, fatigue, insomnia/sleep problems, impatience, headache, difficulty concentrating). It is possible that nicotine withdrawal symptoms could affect a pre-existing mental health condition. These symptoms will be monitored at each visit.

New pregnancy or intention to become pregnant: Nicotine, from cigarettes and from e-cigs, is known to be harmful to the developing human fetus. Women who are pregnant or are nursing a child may not participate in this research study. Females capable of becoming pregnant will be administered a pregnancy test prior to beginning the research. Participants must agree to take reasonable and necessary precautions against becoming pregnant during the period of the investigation.

Spirometry: Risks associated with spirometry may include shortness of breath, dizziness, headache, and on rare occasions fainting while doing the breathing test. Every effort will be made to limit these effects during the procedure. Participants with medical conditions that may place them at increased risk are being excluded.

Loss of confidentiality: There is a risk of loss of confidentiality if information is obtained by someone other than the investigators. Precautions will be taken to prevent this including direct coding of data in REDCap.

Randomization in clinical trials: Participants will be assigned to a research intervention by chance. The research intervention they receive may prove to have more side effects than the other research intervention(s).

Questionnaires: It is possible that some of the questions in the questionnaires may make participants uncomfortable. They will be instructed that they are free to skip any questions that make them uncomfortable. In addition, participants will be provided with a list of phone numbers for organizations that can provide information and referrals should they need them.

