Procedure for suicide risk at all visits where QIDS questionnaire is administered: If participants indicate an answer of > 0 on item 12 of the QIDS questionnaire, the MINI Suicide module will be administered. Scores of ≥ 9 on the MINI Suicide module will require an assessment with a licensed clinician to document a clinical plan and a determination of retention or termination from the study.

Procedures during COVID-19:

Visit 2 will be completed in-person. Participants will be screened for COVID-related symptoms using a modified version of the Patient Screening Questions from the Penn State Health website. The written informed consent process will take place in person using the paper Consent Form HRP-580 uploaded in the "Consent Forms and Recruitment Materials" section of the IRB application. During this process, the usual discussion of procedure, risks, side effects, confidentiality, voluntary participation, and right to refuse participation without prejudice will be explained to the participant. Participants must be capable of understanding the nature of this study, its potential risks, discomforts and benefits before signing consent. Participants will receive a signed copy of the form.

Participants will be asked to provide photo ID to verify the age given in Screener 2. They will have to complete the final eligibility requirements at this visit in accordance with the inclusion/exclusion criteria mentioned above:

1. Obtain urine sample for pregnancy determination for women of child-bearing potential (those who have had a period in the past 12 months) and who have not had a hysterectomy
2. Measure exhaled CO
3. Measure vital signs (blood pressure and heart rate)

Participants will be asked for their cigarette log from the prior week. Additional biomeasures will be obtained (e.g., pulmonary function tests, weight, height) as outlined in Revised Table 1.

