ask about the number of e-cig uses, number of cigarettes smoked, and any non-study cigarettes smoked. During the first week of the online survey, participants will also be asked about nicotine withdrawal symptoms. If participants do not have a reliable cell phone and internet access they will complete the information on paper logs.

Phone Call (Week 1)

Study staff will call participants to check in on their use of the study cigarettes/e-cig, remind them to use the study products, document any adverse events, and remind them to fill out their e-cigarette and cigarette use log on paper and through the online surveys. If any data on the e-cigarette and cigarette use log online survey is missing it will be collected over the phone with the participant.

Visit 4-7 (Weeks 4, 8, 12, 16)

Participants will return their e-cig and cigarette use log, and have a comprehensive set of measures recorded according to the visit (Table 1). Measures will be completed electronically on a participant computer via REDCap or administered by a study coordinator. Participants will be given a laptop with access only to the internet and an individualized REDCap survey will be opened so they can complete direct data entry. Women of child bearing potential will be retested for pregnancy at Visits 5 and 7.

The study staff will give participants e-cig and cigarette use logs and instruct them to record daily use at each visit. All participants will be asked about their use of other nicotine/tobacco products and if they vaped/smoked any other substances other than nicotine/tobacco at each visit as this could affect the urine biomarkers collected during the study (e.g. carbon monoxide and cotinine levels). Participants will be encouraged/provided advice to substitute some of their cigarettes with their e-cigarette.

Participants will receive a 4-week supply of research cigarettes (130% of daily consumption) and e-liquid pods to last approximately 28 days until the next appointment. Participants will be asked to return all opened, unopened and empty cigarette packs and all used/unused e-liquid pods to the study center at each visit in order to monitor use.

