Visits 3-5 and 7 will be completed in-person. Participants will be screened for COVID-related symptoms using a modified version of the Patient Screening Questions from the Penn State Health website. Remote Visit 6 will be completed remotely over Zoom or the telephone. Questionnaires for visits outlined in Revised Table 1 will be sent to the participant via a survey link before the in-person visit. Participants will be encouraged to complete the questionnaires 2 hours before the visit, but will have up to 24 hours to complete them after the visit. Participants will return their e-cig and cigarette use log. Biomeasures will be taken as outlined in Revised Table 1. No biomeasures will be collected at Remote Visit 6. Women of child bearing potential will be retested for pregnancy at Visits 5 and 7.

The study staff will give participants e-cig and cigarette use logs and instruct them to record daily use at each visit. All participants will be asked about their use of other nicotine/tobacco products and if they vaped/smoked any other substances other than nicotine/tobacco at each visit as this could affect the urine biomarkers collected during the study (e.g. carbon monoxide and cotinine levels). Participants will be encouraged/provided advice to substitute some of their cigarettes with their e-cigarette.

Participants will receive a 4-week supply of research cigarettes (130% of daily consumption) and e-liquid pods to last approximately 28 days until the next appointment. At Visit 5, participants will receive an 8-week supply of e-cigarettes and cigarettes due to Remote Visit 6 being a remote visit. Participants will be asked to return all opened, unopened and empty cigarette packs and all used/unused e-liquid pods to the study center at each visit in order to monitor use.

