15.4 Availability of medical or psychological resources

All of our participants will be seen by appropriately trained research staff and research nurses in the Clinical Research Center while in the study. We have established a protocol for assessing suicide risk that requires the availability of a licensed psychiatrist to evaluate participants if they indicate any score on the MINI suicide ≥ 9 at screening or follow-up. Any score on the QIDS questionnaire > 0 will trigger the study staff to complete the MINI Suicide module. Scores ≥ 9 on the MINI will trigger a psychiatric assessment. Any urgent health problem will require accompanying the participant to the ER, which is located in the same building.

Procedures during COVID-19:

If a psychiatric assessment is triggered during a remote visit, the study psychiatrist will contact the participant over the phone or Zoom.

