19.0 Study Monitoring, Auditing and Inspecting

19.1 Study Monitoring Plan

19.1.1 Quality Assurance and Quality Control

The overall responsibility for data quality and study conduct lies with the PI. Data will be collected from participants and coded directly by either using the REDCap survey tool (participant entered data) or through REDCap data entry forms (researcher entered data). The codes that link the name of the participant and the study ID will be kept confidential in REDCap. Any paper forms (consent) will be securely locked in the research offices of the PI. Any additional data that is generated (i.e., electronic PFT), will be stored electronically on the PHS server in password protected files.

Study data will be managed using REDCap (Research Electronic Data Capture). REDCap is a secure web application designed to support data capture for research studies, providing user-friendly web-based case report forms, real-time data entry validation (e.g. for data types and range checks), audit trails and a de-identified data export mechanism to common statistical packages (SPSS, SAS, Stata, R/S-Plus). The system was developed by a multi-institutional consortium which includes The Pennsylvania State University and was initiated at Vanderbilt University. The database is hosted at the Penn State Hershey Medical Center and College of Medicine data center, which will be used as a central location for data processing and management. REDCap data collection projects rely on a thorough study-specific data dictionary defined in an iterative self-documenting process by all members of the research team. This iterative development and testing process results in a well-planned data collection strategy for individual studies.

REDCap is HIPAA compliant. Data are stored on a secure server; data in REDCap are encrypted; access to the database requires authentication (a unique username and password); data are accessed based on the individual's role on the project; every interaction with the data is logged, creating an audit trail.

Data quality tools included in REDCap will be utilized to identify incorrect data types, out of range data and outliers. Data that will be entered by participants directly will be reviewed for completeness. Out of range values will be identified immediately when the participants are completing online data forms to reduce keying errors.

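### A skipped QIDS suicide item starts no risk check under section 7.2, and section 15.4 states a different trigger for the same check

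*Combined protocol and SAP*

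**What the plan says.** **Right to skip.** Section 10.0, under Questionnaires, states: "They will be instructed that they are free to skip any questions that make them uncomfortable". No safety item is exempted.

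**Operative trigger.** Section 7.2 sets the suicide-risk procedure for every visit with a QIDS, and repeats it under the COVID-19 procedures: "If participants indicate an answer of > 0 on item 12 of the QIDS questionnaire, the MINI Suicide module will be administered". A MINI Suicide score of 9 or more then leads to a clinician's assessment and a decision on whether the participant stays in the study.

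**Second trigger.** Section 15.4 says: "Any score on the QIDS questionnaire > 0 will trigger the study staff to complete the MINI Suicide module". It names no item. The threshold of 9 on the MINI is the same as in 7.2.

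**How forms are completed.** Under standard procedures, section 7.2 says: "Measures will be completed electronically on a participant computer via REDCap or administered by a study coordinator". Under the COVID-19 procedures the forms go out by survey link. Participants are encouraged to finish before the visit, "but will have up to 24 hours to complete them after the visit".

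**Remote visits.** Section 15.4 adds: "If a psychiatric assessment is triggered during a remote visit, the study psychiatrist will contact the participant over the phone or Zoom".

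**Completeness.** Section 19.1.1 says: "Data that will be entered by participants directly will be reviewed for completeness". It does not say when, or what follows if an item is missing.

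**The concern.** Everyone enrolled meets MINI criteria for a current or lifetime mood, anxiety, psychotic or eating disorder (section 3.1). With 60 per arm (section 8.1), arms 3 and 4 put 120 of the 240 straight onto very low nicotine cigarettes, and the 60 in arm 4 also receive zero-nicotine e-cigs. Section 2.1 says the effects of immediate switching in this population are not known, and the team's own reassuring mental-health results in section 2.2 come from a gradual reduction. Section 10.0 accepts the risk: "It is possible that nicotine withdrawal symptoms could affect a pre-existing mental health condition".

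After screening, the QIDS rule is the only stated route from a scheduled questionnaire to the suicide module. A participant troubled by suicidal thoughts may be among those most likely to find item 12 uncomfortable. That is a judgement, not a figure from the documents. If it is right, a blank is less reassuring than an answer of 0, yet section 7.2 has the same result for both: no module. At stake is a missed or late suicide-risk assessment. A smaller cost is that the suicidal-ideation line in the committee report (section 9.2) could look complete when some people never answered.

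**Working it through.** No formula applies to the main point. The check is to apply each rule, as written, to the possible QIDS responses.

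| QIDS response | Section 7.2 (item 12 above 0) | Section 15.4 (any QIDS score above 0) |
|---|---|---|
| Item 12 above 0 | Module given | Module given |
| Item 12 = 0, another item above 0 | No module | Module given |
| Item 12 blank, another item above 0 | No module | Module given |
| Item 12 blank, all other items 0 or blank | No module | No module |
| All items 0 | No module | No module |

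1. The rules disagree in rows 2 and 3.
2. Section 7.2 sends nobody with a blank item 12 to the module (rows 3 and 4).
3. Section 15.4, read literally, covers row 3 but still misses row 4. Read as shorthand for item 12, it covers neither.

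**Does another section close the gap?**

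- Section 19.1.1 flags out-of-range values immediately, but its completeness review has no timing, no action and no link to suicide risk.
- Section 7.2, Phone Call (Week 1), recovers missing entries in the online product-use log by telephone. Nothing comparable exists for a missing suicide item.
- The Visit 1 MINI suicide assessment does not depend on the QIDS, so the gap begins after screening.
- The remote clause in 15.4 covers an assessment triggered during a remote visit. It does not cover a form submitted later.

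**Ceiling on forms exposed.** Inputs: 240 randomised (section 8.1) and QIDS at Visits 4, 5, 6 and 7 after randomisation (Table 1).

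- All post-randomisation forms, full retention: 240 x 4 = 960.
- Forms at Visit 6, fully remote under the COVID-19 procedures: 240 x 1 = 240, and 240 / 960 = 25%.

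The 25% is the share at a fully remote visit, not the share that can be completed away from staff. The COVID-19 text applies the survey link and the 24-hour window to Visits 4, 5 and 7 as well. QIDS forms before randomisation are not counted, although the rule applies to them too. Without a skip rate, neither figure estimates how many blanks will occur.

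**The case against.** The strongest reply is that the operative procedure is clear. Section 7.2 names the item and the next step under its own suicide-risk heading, whereas 15.4 describes resources and is loosely worded. Read literally, 15.4 would send anyone with any positive QIDS answer to the module, which is implausible in this sample and would in any case err on the safe side. That reading of 15.4 is probably right. It makes the mismatch an easy correction, but it also removes the only text that might have caught a blank.

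A second reply is that the protocol only summarises operations. Sections 15.4 and 15.5 refer to an established suicide-risk protocol and to SOPs that are not in the document, and a coordinator who administers the forms may notice a blank. This stands as a limit on the claim: the text shows that no follow-up is stated, not that none would happen.

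Third, other safeguards exist: the MINI suicide assessment and the exclusions at screening, the other mood scales, adverse-event questions at each visit, weekly Safety Monitor review, referral numbers, and committee review of suicidal ideation. They lower the risk, but none says what to do when item 12 is blank.

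Fourth, the 24-hour window delays a positive item 12 as much as a blank one, and the COVID-19 procedures are temporary. Both points are fair. The window aggravates the gap but does not create it, since 7.2 has the same wording under standard procedures.

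Last, following up a blank puts some pressure on the freedom to skip. That is a real trade-off, and it is acceptable if the participant can still decline when asked.

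**Conclusion.** The concern holds. Sections 7.2 and 15.4 state different triggers for the same suicide-risk module, and under the more specific rule a skipped item 12 leads to no check. Nothing else in the protocol supplies the missing instruction.

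The size cannot be estimated because no skip rate is given. The figures of 960 and 240 forms are ceilings that assume full retention; the 240 also assumes that every Visit 6 is held under the COVID-19 procedures. The conclusion rests on the protocol text alone, and an unseen SOP could already cover the point. If so, the protocol should say so. This is a participant-safety matter and does not affect the primary NNAL analysis. It should be corrected, because following 7.2 as written gives the worse safety result and the correction is cheap.

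**What to change.** - **One trigger.** State the same rule in 7.2 (both the standard and the COVID-19 text) and in 15.4: give the MINI Suicide module if item 12 is above 0, and follow up if item 12 is blank.
- **Alert and follow-up.** Set a REDCap alert for a blank item 12. Staff then contact the participant at that visit, or on receipt of a form completed remotely, and either ask the item or offer the module.
- **Right to decline.** Keep the wording in section 10.0. A participant may still refuse when asked, and the refusal is recorded.
- **Reporting.** Add the number of blank item 12 responses beside the suicidal-ideation line in the section 9.2 committee report.

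The cost is one alert, one aligned sentence in each section and one line in the report. There will also be extra staff contacts for items left blank by oversight. These are likely to be few, but the documents give no figure from which to count them.
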